quitting, a multi-site cluster RCT (allocation ratio 2:1) will be used. All promotion sessions will be randomly allocated to either the experimental or the control group. The experimental group will receive medication counselling and NRT samples, while the control group only receive the advice to use NRT. Because smokers who receive NRT sampling will be more likely to participate in the study, the experimental sessions will then recruit more smokers than the control sessions. Hence, the allocation ratio of participants is arbitrarily set at 2:1. To increase comparability between the two groups, the promotion sessions of one hotspot will be randomly allocated to either group. All recruitment and quitting outcomes in the smokers between the experimental and control group will be compared.

9. Subjects

Smokers with the following inclusion criteria will be invited to participate in our RCT: (1) Hong Kong residents, (2) aged 18 to 65 years, (3) have used any tobacco products in the past month, (4) able to read and speak Chinese, (5) have not used NRT for the past month, (6) no severe angina, serious cardiac arrhythmias and hypertension, (7) have not suffered acute myocardial event in the past 4 weeks, (8) neither pregnant nor breastfeeding, (9) not under medication and treatment due to mental illness. To confirm the smoking status, in those who use conventional cigarettes, smokers' exhaled carbon monoxide will be measured on-site. Nurses on truck will measure the blood pressure if smoker is aged over 50 years old, obese by observation, or upon patient requests.

10. Procedures

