In the control sessions, all the above procedures for the experimental group will be applied, except that they will not receive an NRT sample and an instruction card about the use of NRT. Instead, they will be advised to obtain free NRT by enrolling in the SC clinics. Both groups will receive a one-page leaflet provided by the SC clinics.

As this trial is a pragmatic trial, flexible procedures will be adopted based on the actual interaction with the participant. Firstly, the intervention components and filling in of baseline questionnaire may be carried out prior to seeking the consent from the participant if it is deemed more suitable in the situation and can make the procedures run more smoothly. Secondly, if the recruitment venue is not suitable for drug dispensing, the NRT sample and the use instructions will be register-mailed to the participants' address instead of given immediately. All NRT will be prescribed by registered nurses. The research assistant will also contact the participants to confirm that they have received the NRT. This arrangement of mailing the NRT sample complies with the Pharmacy and Poisons Ordinance of the Drug Office.

12. Randomization

We will use cluster randomization based on promotion session as the cluster unit because the procedures of individual randomization are difficult in outdoor areas as found in our pilot RCT. The PI will randomly allocate the promotion sessions within a hotspot to the 2 groups by a list of group allocation which is based on a list of random numbers from Excel programme. Each hotspot will have 2 or more promotion sessions, and each session will last for about 3-4 hours. If a hotspot has 2 promotion sessions on 1 single day, the 2 sessions will be allocated into the same RCT group, and we will organize 2 more promotion sessions in this hotspot on another day.

13. Allocation concealment

All recruitment staff will know the group allocation before each promotion session, so no group concealment can be done.

14. Blinding

Participants cannot and will not be blinded to the intervention. Assessors of the follow-up outcomes and the research analysts will not be involved in the recruitment and intervention delivery, and will be blinded to the group allocation (single blindness).

15. Follow-up

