15.2.3 Participants who do not make an intake appointment

The participants will receive motivational messages from the research assistant around one week after baseline to encourage them to quit and enroll in one of the SC clinics.

16. Indicators and targets

Our targets will be as follows:

1. Train 40 tertiary students to be SCAs
2. Deliver brief SC advice to 2,400 smokers (1,200 in the experimental and 1,200 in the control group)

Experimental group

3. Provide NRT sample to 720 smokers (60% of all the approached smokers), who also consent to the follow-up
4. Motivate 288 smokers (40%) to use any SC services
5. Motivate 144 smokers (20%) to attempt quitting (intended abstinence for at least 24 hours).

Control group

6. 360 smokers (30% of all the approached smokers) will consent to the follow-up.
7. Motivate 72 smokers (20%) to use any SC services
8. Motivate 28 smokers (8%) smokers to attempt quitting

Both groups

9. 108 smokers report abstinence (for the past 7 days) at 6-month follow-up (30% of all

the 360 smokers who use any SC services)

17. Sample size determination

To detect a significant difference of the rate of quit attempt (20% versus 8%) with normal test and a power of 95% and 5% significance level, we need 485 subjects in the RCT (allocation ratio 2:1; 323 vs 162). Based on the method of Eldridge et al. (2006) [26], conservatively assuming that we could recruit 8 participants per session on average and the intra-cluster correlation coefficient was 0.1, the design effect is estimated to be 1.7. Thus, the minimum sample size required for the trial is 825 (=1.7 X 485) participants and 60 sessions in total. With the similar calculation, the required sample size for detecting a significant difference in the proportion of using any SC service is 421. Therefore, our targeted sample size is sufficient to answer the research question.

18. Data analyses

To assess the change of knowledge, attitude and practice of SC due to the participation of the SCA workshop, all the outcomes will be tested by McNemar's test (binary outcomes) and pair-sample t-test (continuous outcomes).

To assess the effect of NRT sampling to the recruitment outcomes, the number of smokers who accept the brief advice or consent for the trial in each promotion session will be the outcome variables of Poisson regression model, with group allocation as the predictor, and total number of approached smokers in that promotion session as the offset variable.

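### Both arms run at the same hotspot on different days, but nothing stops a smoker enrolled at one session from enrolling again in the other arm

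*Combined protocol and SAP*

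**What the plan says.** The unit of randomization is the promotion session. Section 12 says: "The PI will randomly allocate the promotion sessions within a hotspot to the 2 groups by a list of group allocation", and continues: "Each hotspot will have 2 or more promotion sessions, and each session will last for about 3-4 hours". Section 8 gives the reason: "To increase comparability between the two groups, the promotion sessions of one hotspot will be randomly allocated to either group".

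Two provisions bear on smokers who return to the same place:

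- **Same-day rule (Section 12).** For a hotspot visited twice within a day, the rule reads: "the 2 sessions will be allocated into the same RCT group, and we will organize 2 more promotion sessions in this hotspot on another day". No minimum interval is set before that other day.
- **Criterion (5) (Section 9).** Participants must "have not used NRT for the past month". The criterion concerns use of NRT, not receipt of it, and not earlier contact with the trial.

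The nine criteria in Section 9, the procedures in Sections 10-11 and the randomization text in Section 12 do not mention earlier approach, refusal or enrolment.

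For the recruitment outcome, Section 18 specifies a Poisson model with group as the predictor and the "total number of approached smokers in that promotion session as the offset variable". It lists no term for hotspot, session order or earlier contact. Among the process indicators in Section 5, first and repeat contacts are not separated.

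**The concern.** Hotspots are fixed places where smokers gather, so some people met at one session may well be met at another. Because both arms visit the same place, two things can follow.

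**Cross-arm enrolment.** A control participant who has used no NRT remains eligible when the team returns with samples. The sample is free and participants are not blinded. As written, that person can be enrolled a second time, and no rule says which arm they belong to. The likely effect on the quitting outcomes is to pull the arms together. The reverse case is also open: an experimental participant who has not used the sample still meets criterion (5) at a later control session.

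**Unequal depletion.** Section 16 expects 60% of approached smokers to be recruited in experimental sessions and 30% in control sessions. An experimental session therefore removes twice as many people from the local pool. If those people are approached again, they add to the offset but may no longer be recruitable. The control session that follows an experimental one loses more than the experimental session that follows a control one, so random order does not fully cancel the effect. Recruitment is the primary process outcome, and the distortion runs in the direction of its hypothesis.

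**Working it through.** **The plan's own figure.** Section 17 inputs: 8% vs 20%, 95% power, 5% significance (taken as two-sided), ratio 2:1. The pooled rate is (0.08 + 2 × 0.20)/3 = 0.16.

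n(control) = [1.960 × √(0.16 × 0.84 × 1.5) + 1.645 × √(0.08 × 0.92 + 0.20 × 0.80/2)]² / 0.12² = 161.4

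This gives 162 control and 323 experimental, 485 in all, as stated. The design effect is 1 + (8 − 1) × 0.1 = 1.7, and 1.7 × 485 = 824.5, so 825. Neither figure allows for controls who receive the sample.

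**A. Recruitment ratio.** From Section 16: 0.60 and 0.30, a true ratio of 2.0. Assumptions, not in the documents: two sessions of equal size per hotspot, one per arm; half the hotspots in each order; a share r of the second session's smokers was met at the first; people already enrolled are not recruited again but stay in the offset.

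*A1: people who refused before respond like new smokers.*
- Control after experimental: 0.30 × (1 − 0.60r)
- Experimental after control: 0.60 × (1 − 0.30r)

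*A2: people who refused the sample also refuse the control offer, and people who refused the control offer accept only if the sample wins them over.*
- Control after experimental: 0.30 × (1 − r)
- Experimental after control: 0.60 × (1 − r) + 0.30r

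The balanced ratio is (0.60 + second experimental rate)/(0.30 + second control rate).

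| r | A1 | A2 |
|---|---|---|
| 0.1 | (0.60 + 0.582)/(0.30 + 0.282) = 2.03 | (0.60 + 0.570)/(0.30 + 0.270) = 2.05 |
| 0.3 | (0.60 + 0.546)/(0.30 + 0.246) = 2.10 | (0.60 + 0.510)/(0.30 + 0.210) = 2.18 |

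**B. Quit attempts.** Let f be the share of controls who obtain the sample at a later session within the month and then respond like the experimental arm. In the two-session layout only control-first hotspots can produce such people. These hold about half the controls, so f is about 0.5r even if every control met again takes the sample: 5% at r = 0.1 and 15% at r = 0.3. The control rate becomes 8% + 12f points.

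| f | Control rate | Difference | Power at N = 825, design effect 1.7 |
|---|---|---|---|
| 0 | 8.0% | 12.0 points | 95.0% |
| 5% | 8.6% | 11.4 points | 92.2% |
| 15% | 9.8% | 10.2 points | 83.8% |

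Power uses effective arm sizes of 825/3/1.7 = 161.8 control and 323.5 experimental in the same pooled-variance test. At f = 15% the standard errors are 0.0358 (null) and 0.0323 (alternative), and Φ[(0.102 − 1.960 × 0.0358)/0.0323] = 0.838.

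**A and B cannot be added.** A assumes that nobody enrols twice, and B assumes that controls do. If re-enrolment happened freely and each enrolment were counted, the second experimental rate would stay at 0.60. With the A2 control rate, the balanced ratio would then be 1.20/0.57 = 2.11 at r = 0.1 and 1.20/0.51 = 2.35 at r = 0.3. That is an extreme case, because every control met again has to enrol a second time.

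**The case against.** Using both arms at one hotspot is a deliberate choice that makes the groups comparable by place, and nothing here argues against it. The same-day rule keeps the two arms from running at a hotspot on one day, and criterion (5) keeps out anyone who has recently used NRT. The overlap rate may be small. With balanced order the recruitment ratio moves by about 2-9% on an expected doubling, and the effect on quitting is toward the null. All of this stands. It makes the point one of modest and unknown size.

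Three stronger readings are tempting and are not supported.

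- **That the recruitment ratio could be as far off as 2.86 or 1.70.** These are the A2 values at r = 0.3 if every hotspot had the same order: 0.60/0.21 and 0.51/0.30. Allocation within a hotspot is random, so neither is the expected bias, although exact balance of order is not guaranteed.
- **That nothing can be repaired afterwards.** Enrolled smokers give written consent (Section 25) and are followed up by telephone or WhatsApp (Section 15), so duplicate enrolments can be sought by contact number. NRT use in the past month is asked at 1 and 3 months (Section 5), though its source may not be. Session order should follow from session dates. What the listed indicators cannot recover is repeat contact with smokers who never enrolled.
- **That the offset could simply be rebuilt from first-time contacts.** Under Section 10 the ambassadors advise smokers who are willing to talk. Those who walk past count as approached but cannot be asked. Staff also know the allocation (Section 13), so such a tally could be misclassified differently by arm.

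**Conclusion.** The gap is real: as written, an NRT-free control participant qualifies for the sample at a later experimental session and can be counted in both arms. Neither the same-day rule nor criterion (5) closes it.

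The size is unknown, because no document gives an overlap rate. It is a risk, not a demonstrated distortion. On an assumed 10-30% overlap with balanced order and no re-enrolment, the recruitment ratio rises from 2.0 to about 2.03-2.18. Under the separate assumption that 5-15% of controls obtain the sample and respond fully, the quit-attempt difference falls from 12 to 11.4-10.2 points. The second range is close to a worst case for that overlap, since it needs every control met again to be NRT-free, to accept, and to respond fully within the month. With few returning smokers both effects are small. This is a cheap improvement and leaves the within-hotspot design as it is.

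**What to change.** - **Section 9:** add a criterion that the smoker has not previously enrolled in this trial at any session, checked by contact number against the enrolment list.
- **Section 18, quitting outcomes:** analyse each person once, in the arm of first enrolment, and record any sample obtained at a later session.
- **Section 10:** have the ambassadors tally self-reported repeat contacts among smokers who stop to talk. This describes the overlap; it does not replace the offset.
- **Section 18, recruitment outcome:** add a sensitivity analysis restricted to the first session day at each hotspot. The same-day rule means that such a day has one arm only. Alternatively, adjust for the arm of the previous session at that hotspot. A plain session-order term is not enough, because the carry-over depends on which arm came before.

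The document carries the same date as the planned completion. If recruitment has closed, the contact-number matching, the first-enrolment rule and the first-day analysis can still be done.

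**Cost:** a few repeat smokers cannot enrol, and each session needs one extra tally column. The first-day analysis is less precise and gives up the comparison within hotspots, which is why it belongs beside the main analysis and not in its place.

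### Section 13 gives up concealment because recruiters know the arm, but each session's allocation could be concealed until its date, start time, length and staffing are fixed, and the plan states no such lock

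*Combined protocol and SAP*

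**What the plan says.** Section 12 makes the session the randomised unit: "We will use cluster randomization based on promotion session as the cluster unit". On who allocates, it says "The PI will randomly allocate the promotion sessions within a hotspot to the 2 groups by a list of group allocation", with the list built from Excel random numbers. It also says "Each hotspot will have 2 or more promotion sessions, and each session will last for about 3-4 hours".

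A special rule covers two sessions at one hotspot on the same day: "If a hotspot has 2 promotion sessions on 1 single day, the 2 sessions will be allocated into the same RCT group", and then "we will organize 2 more promotion sessions in this hotspot on another day". It does not state which arm the added pair takes or when that pair is scheduled.

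Section 13 is a single sentence: "All recruitment staff will know the group allocation before each promotion session, so no group concealment can be done".

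Three other places bear on this. Section 8 expects that "the experimental sessions will then recruit more smokers than the control sessions" and gives comparability as the reason for allocating sessions within a hotspot. Section 11 says "In the control sessions, all the above procedures for the experimental group will be applied", apart from the NRT sample and its instruction card. Section 14 blinds follow-up assessors and analysts.

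**The concern.** Section 13 treats two things as one. The first is whether the people running a session know its arm while it runs. Here they must, because they either offer the sample or do not. The second is whether the people who decide when a session takes place, how long it lasts and who staffs it know its arm when they decide. In a trial that randomises sessions, allocation concealment concerns the second, and nothing about the first rules it out.

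If the arm is known when a session is arranged, its day, start time, length within the stated range and number of ambassadors can be matched to the arm, deliberately or not. The team also holds a directional expectation (Section 8) and has numerical targets by arm (Section 16). Two kinds of outcome are exposed. Raw numbers approached and recruited are process outcomes in Section 5 and depend on hours and headcount. The quitting outcomes could move if the smokers at a hotspot differ by day or time of day.

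**Working it through.** **1. Is concealment of the session possible?** Section 12 makes the session the unit. Its date, start time, length and roster are all settled before it begins. On Section 11's description, both arms follow the same procedures apart from the sample and card, so nothing there requires the arm to be known when a session is put in the calendar. Concealment up to that moment is feasible.

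**2. Does the plan provide it?** Sections 8 and 10 to 14 contain no statement that dates, start times or staffing are fixed before the arm is released. They name no holder of the list separate from scheduling. Session length is given as a range, and no number of ambassadors per session is set.

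**3. The same-day rule.** Two sessions on one day share an arm, and two more follow on another day. If the purpose is to have both arms at each hotspot, as Section 8 suggests, the second pair takes the other arm. Once the first day's arm is known, the second appears predictable.

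**4. Process outcomes.** Assume a constant rate of *a* smokers approached per hour and the same consent proportion *p* in both arms. Take the extremes of the stated range, 4 hours in one arm and 3 in the other:
- ratio of numbers approached: 4a / 3a = 1.33
- ratio of numbers recruited: 4ap / 3ap = 1.33
- ratio of recruited proportions, which the Section 18 Poisson model estimates because its offset is the number approached: (4ap/4a) / (3ap/3a) = 1.0

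The raw counts move and the proportion does not. A difference in headcount works the same way. The offset's protection is incomplete: ambassadors who know the arm record the denominator (Section 5), and day or time could change *p* itself.

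**5. Quitting outcomes.** The documents give no figure for how quit attempts vary with day or time, so this step is illustrative.

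The plan's sample size comes first (Section 17: 20% vs 8%, power 95%, 5% level, 2:1). With pooled proportion (0.08 + 2×0.20)/3 = 0.16, taken two-sided:
- control n = [1.960·√(0.16×0.84×1.5) + 1.645·√(0.08×0.92 + 0.20×0.80/2)]² / 0.12² = (0.880 + 0.645)² / 0.0144 ≈ 161.4
- that is 162 control and 323 experimental, 485 in total, as stated
- design effect 1 + (8 − 1)×0.1 = 1.7, and 485×1.7 = 824.5, so 825 as stated

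Now suppose there is no true effect, the control rate is 8%, and session arrangement raises the experimental rate by *x*. The effective size is 825/1.7 = 485.3 (161.8 control, 323.5 experimental). The chance of a significant result favouring the experimental arm is Φ[(x − 1.96·SE₀)/SE₁], where SE₀ is the pooled and SE₁ the unpooled standard error:

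| x (assumed) | SE₀ | SE₁ | chance |
|---|---|---|---|
| 2 points | 0.0280 | 0.0271 | about 10% |
| 4 points | 0.0297 | 0.0280 | about 26% |
| 6 points | 0.0313 | 0.0288 | about 48% |

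The nominal value in that direction is 2.5%. These figures show sensitivity. They are not evidence that a shift of any of these sizes would occur.

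**The case against.** The strongest case on the other side is that this is only a missing detail. Session length is stated for both arms, procedures are common, allocation is within hotspot and so controls for site, follow-up assessors are blinded, and the recruitment model is adjusted for the number approached. Much of this stands. The offset does largely protect the recruited proportion. The quitting outcomes are proportions among participants, so hours and headcount do not shift them mechanically. But within-hotspot allocation does not balance day, time or staffing; blinded assessment acts after recruitment; and Section 18 names no adjustment for day or time in the quitting models. Section 13 is also more than silent: it states that concealment cannot be done.

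Several stronger readings are tempting, and the documents do not support them:
- *Sessions are routinely added once a hotspot's first arm is known.* They are added only under the same-day rule, and both days could be booked in advance.
- *The PI works from an open list.* The text does not say who can see the list or whether the PI schedules sessions.
- *Longer sessions could manufacture much of the planned doubling in recruitment.* The target of 720 against 360 is 60% against 30% of 1,200 in each arm, a ratio on equal denominators. A ratio of raw counts under unequal hours is a different quantity and should not be set beside it.
- *Randomisation protects no outcome.* This is not shown.

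It is also fair that a schedule lock leaves recruiters knowing the arm when they approach and consent individuals.

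**Conclusion.** The point holds as a gap in the design. Section 13's conclusion does not follow from its premise, the session-level safeguard is feasible, and the plan does not state it. What remains exposed is the raw number approached, the raw number recruited, and the day-and-time mix of smokers behind the quitting outcomes.

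The effect on raw counts is bounded at about 4/3 from session length alone, assuming a constant approach rate and the extremes of the stated range. No bound can be given for staffing, because no team size is stated. The effect on quitting outcomes cannot be sized from the documents; the 10% to 48% range rests wholly on assumed shifts of 2 to 6 points and on the plan's own 825 participants and design effect of 1.7. The predictability of the added pair is an inference from the aim of comparability. The plan should be changed because the remedy is cheap, not because arrangement by arm is known or intended.

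**What to change.** In Sections 12 and 13, state that:
- for each hotspot, all sessions, including any second-day pair, are listed before the allocation is drawn, with dates, start times, one common length and one common number of ambassadors;
- an existing team member who does no scheduling holds the list and releases the arm only after the calendar and roster are locked;
- any later change to a session is logged with its arm.

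Replace the closing clause of Section 13 with a statement that allocation is concealed until the session schedule is fixed, and that recruiters necessarily know the arm during the session. If both days of a same-day hotspot are already booked in advance, say so, and state which arm the second pair takes.

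The cost is a few sentences, a dated calendar and slightly less freedom to rearrange sessions. The intervention, outcomes and sample size are unchanged. The fix does not remove individual-level recruitment bias. If sessions have already been run, report day, start time, length and number of ambassadors by arm instead.
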